2.4.4.4 Additional efficacy analysis

Not applicable

2.4.5 Analyses of safety data

Safety analyses will be conducted using data of the DBTP and OLTP. The summary of safety results will be presented separately for the DBTP on the safety population and OLTP on the OLT population. Besides, safety analyses performed on the alirocumab exposed period (see [Section 2.1.4](#)) will be conducted on the alirocumab safety population to evaluate long-term safety at the first step analysis.

The analyses performed on the DBTP will be presented by treatment group while the analyses performed on the OLTP or the alirocumab exposed period will be presented by overall patients. No formal inferential testing will be performed. Summaries will be descriptive in nature. All summaries of safety results described below will be presented for each observation period respectively, unless otherwise noted.

General common rules

All safety analyses will be performed using the following common rules:

- Safety data in patients who do not belong to the safety population (eg, exposed but not randomized) will be listed separately
- The baseline value for both double-blind and open-label treatment period is defined as the last available value before the first double-blind IMP injection, except otherwise specified.
- The potentially clinically significant abnormality (PCSA) values are defined as abnormal values considered medically important by the Sponsor according to predefined criteria/thresholds based on literature review and defined by the Sponsor for clinical laboratory tests, vital signs, and ECG (PCSA defined in the document “Analysis and reporting safety data from clinical trials through the Clinical Study Report (CSR) (Version Number: 3.0)” [[Appendix A](#)])

Considering that the threshold defined in the PCSA list for monocytes and basophils can be below the ULN, the following PCSA criterion will be used for the PCSA analysis of monocytes and basophils:

- PCSA criterion for monocytes: >0.7 Giga/L or $>$ ULN (if $ULN \geq 0.7$ Giga/L);

- PCSA criterion for basophils: >0.1 Giga/L or $>$ ULN (if $ULN \geq 0.1$ Giga/L).
- PCSA criteria will determine which patients had at least 1 PCSA during the TEAE period, taking into account all evaluations performed during the TEAE period, including unscheduled or repeated evaluations.
- The treatment-emergent PCSA denominator by group for a given parameter will be based on the number of patients assessed for that given parameter at least once during the TEAE period.
- All measurements, scheduled or unscheduled, fasting or not fasting, will be assigned to analysis windows defined in [Section 2.5.4, Table 2](#) in order to provide an assessment for Week 4 to Week 64 time points.
- In both the DBTP and the OLTP, for quantitative safety parameters based on central laboratory/reading measurements, descriptive statistics will be used to summarize results and change from baseline values by visit and treatment group using analysis windows. Summaries will also include the last on-treatment value and the worst on-treatment value. The last on-treatment value is defined as the last value collected during the treatment period of each observation period (see [Section 2.1.4](#)). The worst on-treatment value is defined as the nadir and /or the peak value during the treatment period of each observation period according to the direction (minimum or maximum) of the abnormality as defined in PCSA list.

Analyses performed according to diabetes status will be done using the CMQ definition (regardless of the ongoing status) ([Section 2.1.1](#)).

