5.2 SECONDARY

The secondary objectives are:

- To evaluate the effect of two treatment regimens of alirocumab on other lipid parameters: apolipoprotein B (Apo-B), non-high-density lipoprotein cholesterol (non HDL-C), total cholesterol (TC), lipoprotein (a) [Lp(a)], high density lipoprotein cholesterol (HDL-C), triglyceride (TG), apolipoprotein A-1 (Apo A-1).
- To evaluate the safety and tolerability of alirocumab 150 mg Q4W and 150 mg Q2W.
- To evaluate the development of anti-alirocumab antibodies
- To evaluate the pharmacokinetics (PK) and pharmacodynamics (PD) profiles of alirocumab 150 mg Q4W and 150 mg Q2W.
- To evaluate the long-term safety in patients receiving open-label alirocumab 150 mg Q4W and 150 mg Q2W.

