11.4.3 Analyses of safety data

See also [Section 9.2](#).

The summary of safety results will be presented by treatment group. No formal inferential testing will be performed. Summaries will be descriptive in nature.

All safety analyses will be performed on the Safety population using the following common rule:

- The baseline value is defined generally as the last available value before the first double-blind IMP injection. For analyses of changes from baseline for laboratory and vital signs parameters, baseline of the last available value before double-blind or open-label IMP injection may be considered.

Safety analyses will be conducted using data of the DBTP. Besides, safety analyses using data of the DBTP and the OLTP (from the first double-blind IMP injection for alirocumab 150 mg Q4W group and alirocumab 150 mg Q2W group, and from the first open-label IMP injection for placebo group) will be conducted to evaluate long-term safety.

The following definitions will be applied to laboratory parameters and vital signs:

- The potentially clinically significant abnormality (PCSA) values are defined as abnormal values considered medically important by the Sponsor according to predefined criteria/thresholds based on literature review and defined by the Sponsor for clinical laboratory tests and vital signs.
- The PCSA criteria will determine which patients had at least 1 PCSA during the TEAE period, taking into account all evaluations performed during the TEAE period, including unscheduled or repeated evaluations. The number of all such patients will be the numerator for the PCSA percentage.

Adverse events (AE) definition:

- **Pre-treatment AEs** are AEs that develop, worsen, or become serious during the PRE-TREATMENT period.
- **Treatment-emergent AEs (TEAEs)** are AEs that develop, worsen, or become serious during TEAE period.
- **Post-treatment AEs** are AEs that develop, worsen, or become serious during the POST-TREATMENT period.

Drug-induced liver injury:

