 - For Alirocumab 150 mg Q4W group and Alirocumab 150 mg Q2W group: (date of last dose of IMP injection (double-blind or open-label) +14 – date of first dose of double-blind IMP injection) / 7, regardless of intermittent discontinuations (see [Section 2.5.3](#) for calculation in case of missing or incomplete data). Non-integer values will be rounded to one decimal place;
 - For Placebo Q2W group: (date of last dose of open-label IMP injection +14 – date of first dose of open-label IMP injection) / 7, regardless of intermittent discontinuations (see [Section 2.5.3](#) for calculation in case of missing or incomplete data). Non-integer values will be rounded to one decimal place;
- The total number of alirocumab IMP injections by patient.

Duration of alirocumab IMP injection exposure will be summarized using number, mean, SD, median, minimum and maximum. In addition, it will be summarized according to the following

categories: ≥ 1 day and <12 weeks, ≥ 12 weeks and <24 weeks, ≥ 24 weeks and <36 weeks, ≥ 36 weeks and <48 weeks, ≥ 48 weeks and <60 weeks, ≥ 60 weeks.

Titration

For the OLTP, the number and percentage of patients with an up-titration at Week 24 will be described. Patients with an up-titration are defined as up-titrated patients according to IRT Week 24 transaction with at least 1 injection of alirocumab 150 mg Q2W afterwards.

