According to protocol, cases of overdose are reported in the AE e-CRF pages and will be described in the AE analysis (see [Section 2.1.4.1](#)).

The mean injection frequency of IMP open-label injections (until and after Week 24 separately) will be summarized according to the up-titration status.

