2.4.6 Analyses of other endpoints

All measurements, scheduled or unscheduled, fasting or not fasting, will be assigned to analysis windows defined in [Section 2.5.4, Table 2](#) in order to provide an assessment for Week 4 to Week 64 time points.

HbA1c parameters will be summarized by analysis visit using number of available data, mean, SD, median, minimum, and maximum for each treatment group during the DBTP and OLTP. For HbA1c in DBTP, summary will be also provided according to the diabetes status at baseline defined in [Section 2.1.1](#). The time profile of each parameter will be also plotted by treatment group with the means and the corresponding SEs for HbA1c in DBTP. The incidence of PCSA at any time during the double-blind TEAE period will be also summarized on safety population by treatment group using descriptive statistics. PCSA for HbA1c will be also provided according to the diabetes status at baseline. The incidence of PCSA at any time during the open-label TEAE period (on OLT population) and during alirocumab exposed TEAE period (on alirocumab exposed population, at first step analysis only) will be also summarized using descriptive statistics. PCSA for HbA1c will be also provided according to the diabetes status at baseline.

Binary endpoints defined in [Section 2.1.5](#) will be described using count and percentage. [REDACTED]

[REDACTED] For the analysis of the time to the first of the 2 consecutive LDL-C, patients without post-baseline LDL-C result or with only 1 post-baseline LDL-C result will not be included.

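### The planned open-label safety tables pool all patients, so no visible adverse-event or PCSA output separates Q4W from up-titrated Q2W after Week 24, although the long-term safety objective names both regimens.

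*SAP*

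**What the plan says.** The last secondary objective in Protocol 5.2, repeated in SAP 1.2.2, is "To evaluate the long-term safety in patients receiving open-label alirocumab 150 mg Q4W and 150 mg Q2W".

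Under Protocol 6.1 and SAP 1.1, all patients receive Q4W from Week 12. Up-titration to Q2W happens at Week 24 only, triggered by the Week 20 LDL-C.

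On presentation, the documents differ:

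- Protocol 11.4.3: "The summary of safety results will be presented by treatment group".
- SAP 2.4.5, general rule: double-blind safety is shown by treatment group, while "the analyses performed on the OLTP or the alirocumab exposed period will be presented by overall patients".
- SAP 2.4.5, common rules, for quantitative central-laboratory parameters in both periods: "descriptive statistics will be used to summarize results and change from baseline values by visit and treatment group using analysis windows".
- SAP 2.4.6, HbA1c: summary statistics up to the "maximum for each treatment group during the DBTP and OLTP".
- SAP 2.4.5.3, hepatitis C: seroconversion is shown by treatment group, and the open-label period is among the listed analysis periods.
- SAP 2.4.5.1: adverse-event denominators are taken within treatment group, and tables are sorted on frequency in the Q4W group.

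SAP 1.5 and 1.6 declare no modification. Up-titration status is used in two visible places, neither a safety table. SAP 2.4.3.1: "the number and percentage of patients with an up-titration at Week 24 will be described". SAP 2.4.3.2: "The mean injection frequency of IMP open-label injections (until and after Week 24 separately) will be summarized according to the up-titration status".

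**The concern.** The objective names two regimens, and the main open-label safety display has one column. That column mixes Q4W time with post-Week 24 Q2W time. It also mixes former placebo patients taking their first alirocumab with patients who already have 12 weeks of exposure. An excess on Q2W would be diluted by the patients who stay on Q4W, and early events in new starters would be diluted by patients who already tolerated the drug.

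This bears on a difference the protocol itself reports. Protocol Section 4 describes the Q4W safety profile as similar to Q2W apart from the frequency and onset of injection-site reactions. A reader of the final report would see one pooled figure and could take it as evidence for each regimen.

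**Working it through.** **1. Which outputs cover up-titrated Q2W?** SAP 2.1.4 and 2.4.5 restrict the alirocumab-exposed period to the first-step analysis. SAP Section 3 cuts first-step safety data at the Week 24 visit (or Day 169). Up-titration occurs at Week 24, so first-step outputs contain essentially no up-titrated exposure. That leaves the second-step open-label tables as the only visible adverse-event display covering Q2W after up-titration, and the general rule pools them.

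**2. Would treatment-group columns separate the regimens?** No. SAP 2.3.2 defines the as-treated group from the double-blind injections. After Week 12 that label no longer identifies the regimen received: a patient from any arm may be on Q4W throughout or on Q2W from Week 24. SAP 2.4.5.3 and 2.4.5.4 also remove by-visit laboratory and vital-sign analyses for the open-label period, which cuts across the by-visit, by-group rule in 2.4.5.

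**3. The plan's own safety sizing (Protocol 11.1, SAP 1.3) reproduces.**

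- Dropout to Week 64 from 30% in 12 months, exponential: 1 − 0.7^(64/52) = 35.5% (stated 36%).
- Patients remaining: 159 × (1 − 0.36) = 101.8 (stated 100).
- Chance of at least one event at rate 0.03 in 100 patients: 1 − 0.97^100 = 95.2% (stated 95%).

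The detection statement applies to the pooled 100, not to either regimen.

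**4. Size of the Q2W group.** With the same hazard, patients reaching Week 24 number 159 × 0.7^(24/52) = 134.9. The up-titrated share is not in the documents, so 10% to 40% is an assumption, as are the event rates of 10% on Q2W and 3% on Q4W. With share f, the pooled rate is 0.10f + 0.03(1 − f).

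| Assumed share f | On Q2W (134.9 × f) | Pooled rate |
|---|---|---|
| 10% | 13.5 | 3.7% |
| 20% | 27.0 | 4.4% |
| 30% | 40.5 | 5.1% |
| 40% | 53.9 | 5.8% |

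This is a simple patient-weighted mix of post-Week 24 experience, with dropout unrelated to up-titration.

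**5. Longest open-label Q2W exposure.** Week 64 − Week 24 = 40 weeks, with the last Q2W injection at Week 62 (Protocol 8.1.2).

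**The case against.** A reader might infer that all open-label safety is pooled and that long-term safety cannot be assessed for either regimen. The documents do not support that. Laboratory, HbA1c and hepatitis C text calls for treatment-group summaries that include the open-label period, so the SAP contradicts itself rather than pooling uniformly. Open-label data up to Week 24 are Q4W data for everyone, though they cover only 12 weeks. Up-titration is recorded, so regimen-specific tables could be produced later. What stands is that no visible planned table does so.

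Other objections carry weight:

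- The open-label period can be read as one strategy, Q4W with LDL-C-triggered up-titration, sized on 100 exposed patients in total. A pooled column describes that strategy. The objective still names both regimens, and Protocol Section 4 treats justifying up-titration as part of the rationale.
- Protocol 11.4.3 is brief by design and leaves detail to the SAP. Following its treatment-group wording would not separate the regimens. It shows an undeclared difference, not the remedy.
- The small Q2W group and the 40-week ceiling come from the design. Pooling does not cause them, and extra columns would not remove them.
- Protocol Section 4 reports no dose relationship for adverse events in pooled studies, which used Q2W dosing. SAP 2.4.5.1 already plans open-label injection-site reactions per injection and time from first open-label injection. This helps with differing injection frequency but still mixes regimens and prior exposure.
- Parts of SAP 2.4.5.1, 2.4.6, 2.4.7 and Section 3 are redacted or unreadable, and Appendix B is not in the supplied text. The claim is limited to visible text.

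**Conclusion.** The point holds in limited form. In the visible plan, open-label adverse events and PCSAs follow a pooled rule, and nothing separates Q4W from up-titrated Q2W after Week 24. The planned tables therefore do not deliver the regimen-specific long-term safety that the objective states. The pooled rule is also inconsistent with SAP 2.4.5 (common rules), 2.4.5.1, 2.4.5.3 and 2.4.6, and departs from Protocol 11.4.3 without being listed as a modification.

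The size of the dilution depends wholly on the assumed up-titrated share and the illustrative rates in the table. The firm conclusions are the missing split and the conflicting passages. This should be corrected before the second-step analysis. It does not affect the primary endpoint or trial conduct.

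**What to change.** 1. Reconcile the general rule in SAP 2.4.5 with its own common rules, with 2.4.5.1, 2.4.5.3 and 2.4.6, and with Protocol 11.4.3. Record the result in SAP 1.5 or 1.6.
2. For the second-step open-label analysis, keep the overall column and add two descriptive TEAE and PCSA columns. The Q4W column covers patients never up-titrated, plus up-titrated patients before their first Q2W dose. The Q2W column covers time after up-titration. Assign events to the regimen at onset and show person-time. State which injection starts the Q2W segment.
3. Add one open-label TEAE overview of former placebo versus former alirocumab patients. A split by randomized arm alone would not close the gap.
4. State that open-label Q2W lasts at most 40 weeks and that the regimen columns are not a randomized comparison.

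The cost is SAP wording, a few table columns and a modest new derivation: up-titration status exists per patient, but regimen at onset and person-time must be built. Some columns will be small, and the regimen contrast is confounded by LDL-C, so it must stay descriptive.

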1 OVERVIEW AND INVESTIGATIONAL PLAN

1.1 STUDY DESIGN AND RANDOMIZATION

This is a randomized, double-blind, placebo-controlled, parallel-group, balanced (1:1:1), Alirocumab 150 mg every 4 weeks (Q4W): Alirocumab 150 mg every 2 weeks (Q2W): Placebo Q2W, subcutaneous injection), multi-center phase 3 study to evaluate the efficacy and safety of alirocumab in patients with hypercholesterolemia not adequately controlled with non-statin lipid modifying therapy (LMT) or the lowest strength of statin.

After a screening phase of up to 3 weeks, patients will be centrally randomized (using permuted block randomization schedule) via Interactive Response Technology (IRT) in a 1:1:1 ratio to 1 of the 3 treatment groups. Randomization will be stratified according to background statin therapy (Yes/No). “No statin background” will be also stratified according to background fibrate/ezetimibe therapy (Yes/No), where ‘Yes’ represents fibrate or ezetimibe, and ‘No’ represents diet therapy alone.

The study consists of 5 periods: run-in, screening, double-blind treatment period (DBTP), open-label treatment period (OLTP), and follow-up.

- A run-in period of 4 weeks. Patients will be treated by stable non-statin LMTs or stable daily atorvastatin 5 mg. Patients who will have already been treated by stable non-statin LMTs or stable daily atorvastatin 5 mg for at least 4 weeks will be able to skip this period.
- A screening period of up to 3 weeks.
- A DBTP of 12 weeks. Patients will receive double-blind treatment as follows,
 - Alirocumab 150 mg Q4W alternating with placebo Q4W OR
 - Alirocumab 150 mg Q2W OR
 - Placebo for alirocumab Q2W
- An OLTP of 52 weeks. All patients will receive alirocumab 150 mg Q4W from the start of OLTP. At Week 24, the up-titration to alirocumab 150 mg Q2W will be conducted through IRT only under the following circumstances:
 - In patients with heterozygous familial hypercholesterolemia (heFH) or in patients with non-familial hypercholesterolemia (non-FH) with documented coronary heart disease (CHD), low-density lipoprotein cholesterol (LDL-C) is ≥ 100 mg/dL (2.59 mmol/L) at Week 20.
 - In patients with non-FH classified as primary prevention category III, LDL-C is ≥ 120 mg/dL (3.10 mmol/L) at Week 20.
- A follow-up period of 8 weeks.

Approximately 159 subjects (53 subjects per treatment group) will be recruited and randomized

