- The open-label RESIDUAL TREATMENT period: defined as the time from the day of last dose of open-label IMP injection +22 days up to the day of last dose of open-label IMP injection +70 days (10 weeks).
- The open-label POST-TREATMENT period: defined as the time starting the day after the end of the open-label TEAE period (i.e., 71 days after the day of last dose of open-label IMP injection).

Observation periods below will be analyzed at the first step analysis only.

- The alirocumab exposed TEAE period is defined as follows :
 - For alirocumab 150 mg Q4W group and alirocumab 150 mg Q2W group: The time from the first dose of double-blind IMP injection to the last dose of IMP injection (double-blind or open-label) + 70 days (10 weeks).

- For placebo Q2W group: The time from the first dose of open-label IMP injection to the last dose of open-label IMP injection + 70 days (10 weeks).

The alirocumab exposed TEAE period will include:

- The alirocumab exposed TREATMENT period: defined below:
 - For alirocumab 150 mg Q4W group and alirocumab 150 mg Q2W group: The time from the first dose of double-blind IMP injection to the last dose of IMP injection (double-blind or open-label) + 21 days.
 - For placebo Q2W group: The time from the first dose of open-label IMP injection to the last dose of open-label IMP injection + 21 days.
- The alirocumab exposed RESIDUAL TREATMENT period: defined below:
 - For alirocumab 150 mg Q4W group and alirocumab 150 mg Q2W group: The time from the day of last dose of IMP injection(double-blind or open-label) +22 days up to the day of last dose of IMP injection(double-blind or open-label) +70 days (10 weeks).
 - For placebo Q2W group: The time from the day of last dose of open-label IMP injection +22 days up to the day of last dose of open-label IMP injection +70 days (10 weeks).

The double-blind on-study observation period is defined as the time from the day of first dose of double-blind IMP injection until the last protocol planned double-blind visit of the patient. The last protocol planned double-blind visit is defined as the follow-up visit if done, or a maximum of 20 weeks after the randomization of the patient, for patients not proceeding into OLTP. For patients proceeding into OLTP, the last protocol planned double-blind visit is defined as the end of double-blind treatment period visit (Week 12).

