2.1.4.1 Adverse events variables

AEs (including SAEs and AESI) are recorded from the time of signed informed consent until the end of the study. All AEs diagnosed by the Investigator, irrespective of the result of the adjudication for CV events, will be reported and described.

All AEs will be coded to a lower-level term (LLT), preferred term (PT), high-level term (HLT), high-level group term (HLGT), and associated primary system organ class (SOC) using the version of Medical Dictionary for Regulatory Activities (MedDRA) currently in effect at Sanofi at the time of the database lock for the first step analysis.

Adverse event observation period

- Pre-treatment AEs are AEs that developed or worsened or became serious during the pre-treatment period.
- Double-blind TEAEs are AEs that developed or worsened or became serious during the double-blind TEAE period.
- Double-blind post-treatment AEs are AEs that developed or worsened or became serious during the double-blind post-treatment period.
- Open-label TEAEs are AEs developed or worsened or became serious during the open-label TEAE period.
- Open-label post-treatment AEs are AEs that developed or worsened or became serious during the open-label post-treatment period.
- Alirocumab exposed TEAEs are AEs developed or worsened or became serious during the alirocumab exposed TEAE period.

AESI include the following AEs:

AESIs are AEs (serious or non-serious) that need to be monitored, documented, and managed in a pre-specified manner described in the protocol. In this study, AESIs are the following (their complete descriptions are provided in the protocol):

- Local injection site reactions, selected using e-CRF specific tick box on the AE page;
- Allergic events:
 - General allergic events will be tabulated. Events will be selected using standardized MedDRA query (SMQ) "hypersensitivity" (broad and narrow) excluding the following preferred terms linked to local injection site reactions ("infusion site dermatitis", "infusion site hypersensitivity", "infusion site rash", "infusion site urticaria", "injection site dermatitis", "injection site hypersensitivity", "injection site rash", "injection site urticaria" and "injection site vasculitis");

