2.4.5.3 Analyses of laboratory variables

The summary statistics (including number, mean, median, Q1, Q3, SD, minimum and maximum) of all laboratory variables (central laboratory values and changes from baseline) will be calculated for each visit or study assessment (baseline, each post-baseline value of the treatment period, last on-treatment and worst on-treatment value) by treatment group. In addition, for some parameters of interest, mean changes from baseline with the corresponding SE could be plotted over time (at same time points) in each treatment group. This section will be organized by biological function as specified in [Section 2.1.4.3](#). For glucose, only fasting samples will be summarized.

The incidence of PCSAs (list provided in [Appendix A](#)), as well as ALT increase as defined as AESI and hemoglobin decrease from baseline $\geq 15\text{g/L}$ (see [Section 2.1.4.1](#)), at any time during the TEAE period will be summarized by biological function and treatment group irrespective of the baseline level and/or baseline level and/or according to the following baseline status categories:

- Normal/missing
- Abnormal according to PCSA criterion or criteria

Glucose (quantitative summary and PCSA) will also be analyzed, overall and according to the diabetes status at baseline defined in [Section 2.1.1](#).

CPK (PCSA) will also be analyzed, overall and according to prior history of side effects caused by statin.

For parameters for which no PCSA criteria are defined, similar table(s) using the normal range will be provided.

Hepatitis C

Analysis of hepatitis C will be done for patients below according to analysis period.

- DBTP (Hepatitis C planned to be tested for patients who prematurely discontinue study treatment during DBTP) in safety population.
- Alirocumab exposed period (at first step analysis only) (Hepatitis C planned to be tested for patients who prematurely discontinue study treatment during alirocumab exposed period) in alirocumab safety population.
- OLTP: in OLT population.

The number and percentage of patients with a post-baseline seroconversion for hepatitis C test will be provided by treatment group in post-baseline (including the TEAE and post TEAE periods) as well as in the TEAE period alone. Post-baseline seroconversion is defined for patients with a negative baseline status who had either a “positive ribonucleic acid” (RNA) or a “confirmed

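### In the alirocumab exposed safety tables, former placebo patients keep a baseline taken 12 weeks before their first alirocumab dose, so persisting placebo-period shifts enter the baseline-dependent summaries

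*SAP*

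**What the plan says.** SAP 2.4.5 introduces its conventions with "All safety analyses will be performed using the following common rules", and one of them reads "The baseline value for both double-blind and open-label treatment period is defined as the last available value before the first double-blind IMP injection", closing with a clause that leaves room for exceptions stated elsewhere.

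SAP 2.1.4 defines a third safety window beside the double-blind and open-label ones, the alirocumab exposed period, for use at the first-step analysis. In the two alirocumab arms it opens at the first double-blind injection. In the placebo arm it opens later: "For placebo Q2W group: The time from the first dose of open-label IMP injection to the last dose of open-label IMP injection", with follow-up days added. SAP 2.4.5 presents this period for patients overall, not by randomized arm.

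SAP 2.4.5.3 and 2.4.5.4 carry the double-blind laboratory and vital-sign tables over to the exposed period with a single exception, the by-visit analyses. The laboratory tables cover PCSAs, "as well as ALT increase as defined as AESI and hemoglobin decrease from baseline" of at least 15 g/L, split where relevant by baseline status.

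Protocol 11.4.3 is more flexible. For laboratory and vital-sign changes it says that a "baseline of the last available value before double-blind or open-label IMP injection may be considered". The SAP does not visibly take this up, and its Sections 1.5 and 1.6 on modifications are marked not applicable.

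**The concern.** The exposed period is meant to describe what happens once a patient is on alirocumab. For two arms, the baseline is the last value before alirocumab starts. For the third, it is the last value before placebo starts, and a "A DBTP of 12 weeks" lies between that value and the first alirocumab dose. Pooling the arms puts two meanings of change from baseline in one column, and the reader cannot separate them.

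Elsewhere the SAP does restart the clock at first alirocumab for former placebo patients: for the exposed window itself (2.1.4), for duration of exposure (2.4.3.1) and for time to first injection site reaction (2.4.5.1). The baseline is the element left behind.

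At stake is the attribution of laboratory, vital-sign and ECG changes in a safety summary produced at the first step. Protocol 11.5 says that data to 24 weeks are required for the Japanese application.

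**Working it through.** The point rests on no calculated figure in the plan. It follows from dates and definitions.

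**Dates (Protocol 1.2)**

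| Arm | Safety baseline | First alirocumab | Gap |
|---|---|---|---|
| Q4W, Q2W | last value before Day 1 injection | Day 1 | none beyond pre-dose sampling |
| Placebo | last value before Day 1 injection | Day 85 | 85 − 1 = 84 days |

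For HbA1c, SAP 2.1.5 fixes baseline at Week -3, so the nominal gap in the placebo arm is 3 + 12 = 15 weeks.

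**Share affected.** 53/159 = 33.3%, if every placebo patient enters the open-label period.

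**What the interval contains.** The first-step safety cut-off is the Week 24 visit, Day 169 (SAP 3). Between first open-label dosing and that visit, the flow chart schedules hematology, chemistry and liver panel once, at Week 24. For a former placebo patient, change from baseline then spans 169 − 1 = 168 days, and 84 of these, half, were on placebo.

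**Effect on a mean.** Let m be the mean change in the 106 patients of the alirocumab arms. Suppose former placebo patients change by m on alirocumab plus a persisting drift d on placebo. Pooled mean = (106m + 53(m + d))/159 = m + 53d/159 = m + d/3.

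**Effect on the hemoglobin count.** Let a be the change from Week 0 to Week 12 and b the change after that, in g/L. The SAP counts a patient when a + b ≤ −15. The change on alirocumab is b.
- If a is negative, a patient with b above −15 can still be counted.
- If a is positive, a patient with b ≤ −15 is missed whenever b > −15 − a.

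**Effect on the ALT criterion (SAP 2.1.4.1).** It is 3 × ULN when baseline is below ULN, and 2 × baseline otherwise. Take a patient below ULN at Week 0 whose Week 12 value is x × ULN, with x ≥ 1. The Week 0 baseline sets the limit at 3 × ULN; the Week 12 baseline would set it at 2x × ULN. These agree at x = 1.5. Below that, the plan's rule can miss a doubling on alirocumab; above it, the plan's rule counts more.

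**What does not depend on this baseline**
- AE tables: "Alirocumab exposed TEAEs are AEs developed or worsened or became serious during the alirocumab exposed TEAE period". No baseline measurement enters.
- Changes that resolved before the first open-label dose: only values inside the window are used.
- Fixed-threshold PCSAs tabulated irrespective of baseline.

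SAP 2.5.3 shows that some PCSAs do include a change-from-baseline condition. Appendix A is not shown, so these cannot be listed. HbA1c appears in the exposed period only as PCSA incidence (SAP 2.4.6); whether its criterion uses baseline cannot be checked.

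**Illustrative size.** The documents give no rate of persisting placebo-period shifts. If 2%, 5% or 10% of the 53 had one that altered a classification, then 53 × 0.02 = 1.1, 53 × 0.05 = 2.7 or 53 × 0.10 = 5.3 patients would be affected, or 0.7, 1.7 or 3.3 percentage points of 159. These rates are assumptions.

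**The case against.** The strongest reply has three parts.

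First, a single pre-randomization baseline is an accepted convention. The SAP sentence allows exceptions and names the double-blind and open-label periods, not the exposed one. The protocol permits an open-label baseline, and redacted text or Appendix A might specify it. This stands in part: an exception in unseen text cannot be excluded. But the rule is declared common to all safety analyses, the visible exposed-period sections except only by-visit tables, and a permitted option is not a specified one.

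Second, the consequence is small. The summaries are descriptive, the exposed analysis is first-step only, and double-blind safety is shown separately by arm, so shifts arising on placebo are visible there. This stands, and it keeps the point minor.

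Third, any carry-over counts against alirocumab and is therefore conservative. This does not stand in general: a rise on placebo followed by a fall on alirocumab, or the reverse, can cancel.

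A reader might go further and infer that everything that happened on placebo is counted as alirocumab-emergent. The documents do not support that. Investigator-reported AEs must begin, worsen or become serious inside the window, and resolved changes never enter. The exposure is limited to persisting shifts in baseline-referenced outputs.

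**Conclusion.** The point holds in this limited form. On the visible text, up to 53 of 159 patients in the pooled exposed-period tables have a baseline 84 days before their first alirocumab dose. A persisting placebo-period shift enters change to last or worst value, the hemoglobin decrease, the ALT event of special interest, any PCSA defined by change, and laboratory PCSA and ECG tables by baseline status. The distortion can run in either direction.

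The size in means is d/3 for a drift d, assuming that all randomized patients contribute. The number of affected events cannot be estimated from the documents. Efficacy, alpha and power are untouched. This is an inexpensive improvement, not a threat to the trial's conclusions.

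**What to change.** In SAP 2.4.5, add that for the alirocumab exposed analyses baseline is the last available value before the first alirocumab injection. For the placebo group this means the last value before the first open-label injection:

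- **Blood tests:** the Week 12 sample, which Protocol 10.1.3.7 and 10.1.4.1 require before dosing.
- **Vital signs, weight, ECG:** the last value confirmed as pre-dose. The Week 12 visit sections guarantee pre-dose timing only for blood, and Protocol 8.1.2 places all assessments before injection only under its double-blind heading.
- **HbA1c:** the same definition must be added in SAP 2.1.5 and 2.4.6, because a change in 2.4.5 would not reach the Week -3 baseline fixed there.

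Protocol 11.4.3 already allows this for laboratory and vital-sign data. It names no such option for ECG, and Protocol 9.3.2 sets Week -3 for HbA1c, so those two changes should be recorded in the SAP's modification sections.

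Leave the common baseline for the double-blind and open-label tables as it is. Those periods are not defined by first exposure to alirocumab, and in the open-label period a common reset at Week 12 would remove the earlier alirocumab effect from the two active arms.

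The cost is a few sentences and a second baseline flag, with no new data. The drawback is that former placebo patients carry different baselines in different tables; a footnote on each affected table should say so.
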